1.1 Background and rationale

Health benefits and interest of carotenoids

Carotenoids are a group of C-30 to C-50 terpenoids found predominantly in many plants and several types of fungi, which are able to produce them. A limited number and amount of carotenoids can also be found in animals, such as in salmon, which accumulate these pigments in their tissues, due to their feeding habits. However, as humans cannot produce carotenoids, diet is the only source of these lipophilic compounds. Around 40-50 carotenoids have been reported to be important for the human diet [1].

Several of these carotenoids, including alpha-and beta-carotene, as well as beta-cryptoxanthin can be metabolized by the human body into vitamin A, and are thus crucial sources of this essential nutrient for vegetarians/vegans, and people not consuming much meat (which is the best dietary source of preformed vitamin A), such as in developing countries. The most predominant natural dietary sources of carotenoids include colored fruits and vegetables, such as bell peppers, tomatoes, or carrots, and green leafy vegetables such as spinach or kale [2, 3]. The consumption of carotenoids within these fruits and vegetables, as well as their blood plasma levels, have been related to the reduction of several chronic diseases, including cardiometabolic complications [4, 5] and even reduction of total mortality [6]. In addition, some carotenoids, especially zeaxanthin and lutein, are associated with reduced severity of age-related macular disease, the major cause of blindness in the elderly [7, 8]. The mechanisms contributing to these beneficial health effects are not always completely understood, but have been suggested to rely in part on the potential to influence cellular signaling cascades, reducing inflammation [9, 10], strengthening the body's own antioxidant system [11], impacting intercellular gap-junction communication [12] and regulating apoptosis [4, 13].

Despite that these noted effects are generally ascribed to the intake of carotenoids within the normal diet, it also has to be stated that these health effects could not be confirmed in studies serving isolated carotenoids at higher doses, such as in form of supplements [14, 15]. These surprising results have been explained by the hypothesis that isolated antioxidants, when supplemented at high doses, behave differently than when served within whole fruits or vegetables, where they are occurring together with additional, perhaps synergistically acting anti-oxidants, such as vitamin C and E, and may cause adverse effects especially less healthy subjects including smokers. 3

Despite the still ongoing controversial discussion on their bioactivity, carotenoids are still advertised as health promoting compounds, and found in many dietary supplements, either alone or combined with other nutrients in multivitamin/ multimineral supplements.

The bioavailability of carotenoids

Before reaching their place of action and storage, carotenoids have to go through processes and pathways that are involved in the release from food matrix, digestion, absorption, plasma transport and tissue uptake. The amount of carotenoids released from the food matrix, absorbed and available for physiological functions defines the bioavailability of an individual carotenoid [16]. The percentage of ingested carotenoids that are potentially available for absorption, i.e. bioaccessibility, depends on the release from the food matrix during digestion and its solubilization, i.e. emulsification [16].

While data with respect to carotenoid intake is frequently available, much less is known on dietary factors impacting their bioavailability, including a) changes during gastro-intestinal digestion and b) uptake by the gastro-intestinal epithelium, among others. In general, carotenoid absorption is low (usually ca. 5-20%), owing to the fact that these liposoluble micronutrients and phytochemicals need to be emulsified prior to their small intestinal uptake.

Among the factors that are known to improve carotenoid absorption are dietary lipids [17], usually attributed to enhanced micellarization of carotenoids, and the negative impact of dietary fibers, possibly inhibiting the release of carotenoids from the matrix or due to increased viscosity [1, 18]. Recently, and because of another research project in Luxembourg the potential negative effects of divalent minerals on carotenoid bioaccessibility/bioavailability have been highlighted [19-21].

Role of proteins and relation to carotenoid bioavailability

A factor that so far has received very little attention is proteins. It has been speculated that proteins can aid in emulsifying apolar dietary constituents during digestion [22, 23]. In fact, proteins proved to be effective emulsifiers by having both hydrophobic and hydrophilic groups and reduce oil-water interfacial tension by adsorption to lipid droplet surface [24]. In this respect, proteins go through a structural modification (secondary and tertiary structure rearrangements) in such a way that maximum interaction between hydrophobic segments and the hydrophilic phase is ensured [23, 25]. In addition, it has been reported that the presence of surface active compounds in food matrix constitutes one of prominent factors influencing carotenoid bioavailability [23]. Therefore, the aggregation of adsorbed protein molecules can form protective viscoelastic surface layers and prevents aggregation of lipid droplets (electrostatic and steric repulsion), thus determining emulsion stability [24] required for the formation of micelles. To our knowledge, the interaction of proteins with carotenoids during digestion, absorption, and further biodistribution, targeting to study carotenoid bioavailability, has never been studied systematically. However, we have seen previously *in-vitro* that carotenoids digested with milk resulted in higher bioaccessibility compared to carotenoids digested with oil, which – so our hypothesis – was due to the influence of emulsifying proteins during digestion [26]. Furthermore, preliminary but unpublished results in our own laboratory indicate that, for example, whey proteins can enhance beta-carotene bioaccessibility by a factor of two. This hypothesis has resulted in an accepted FNR-CORE grant (CAROPROT, C16/BM/11320230).

While these *in-vitro* experiments cited above represent a good starting point for hypothesis building and screening, it can only to some extent predict *in-vivo* conditions, and to validate the experimental results obtained we envision a human proof-of-concept nutritional study. Therefore, different proteins and concentrations will be tested and compared *in-vitro* (including whey protein isolate, soy protein isolate, caseinate sodium and gelatine), then two different proteins will be selected for human trial, using up to half of the recommended dietary allowance (RDA) of 60 g/d for adults [27].

1.2 Objectives

The main objective of the study is to investigate the influence of co-consuming two different protein sources on the bioavailability of dietary carotenoids by conducting a postprandial cross-over study.

2. Study Methods

2.1 General procedure

The ITT population is all patients randomized to a diet or control arm whatever the arm they were finally allocated. The Per Protocol population is all patients randomized and allocated to an arm that followed strictly the protocol. Participants with major deviations to the protocol will be excluded from the PP population.

For all other procedures, it is referred to the “study protocol”.

2.2 Primary Endpoints

The main endpoint of the study is the difference in AUC (concentration over time in %) of circulating carotenoids in the plasma triacylglycerol-rich lipoprotein (TRL) fraction between two different protein

sources and control (no protein added). These investigated circulating carotenoids will be lycopene and beta-carotene.

More specifically, the data will be evaluated as follows:

- a) Determination of the AUC, using the trapezoidal method (Excel)
- b) Verifying whether data is normally distributed. If not, log-transformation will be attempted.
- c) Data will be baseline subtracted – conc. at time 0 will be subtracted from all later values. Alternatively, in the frame of a sensitivity analysis, original data will be used (with baseline concentrations as covariate).
- d) Negative concentrations at time points, if occurring, will be treated as “negative area”, i.e. this area will be subtracted from the positive area.
- e) The baseline conc. will be included as a co-variate in the model.

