11. STATISTICAL ANALYSIS

The baseline corrected AUC for carotenoids will be calculated by the trapezoidal approach, using the PK functions plug-in for Microsoft Excel. Negative values, if occurring, will be included as such.

Mean AUC between the test meals will be compared by a repeated measures ANOVA design (i.e. each subject will be compared against himself at 3 time points), followed by post-hoc test comparisons (Fisher protected LSD test) given a significant Fisher-F test. No log-transformation will be carried out, but AUC values will be baseline corrected. Thus, a model with the observed dependent factor baseline-corrected-AUC for each carotenoid (lycopene, beta-carotene) and the triglycerides will be run, with subject, randomization sequence, test meal as fixed factor and baseline carotenoid concentration as a covariate.

Normal distribution will be verified by Q-Q-plots and Kolmogorov-Smirnoff tests.

Non parametrical analysis (Friedman tests followed by individual t-tests) may be chosen in case data is not normally distributed, though based on earlier studies data normally follows normal distribution. Log-transformation will not be carried out.

P-values below 0.05 will be interpreted as statistically significant (2-tailed). Data analysis will be performed with SPSS 19.0 for Windows (SPSS Inc., Chicago IL).

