5.1 Outcome definition

Primary outcomes:

Beta-carotene and lycopene

Beta-carotene and lycopene will be measured in the plasma triacylglycerol rich lipoprotein (TRL) fraction in μM at baseline (0h) and 2h, 3h, 4h, 5h, 6h, 8h, 10h after test meal intake. Using non-compartmental analysis, repeated measures over time of carotenoids will be summarised as postprandial AUC (trapezoidal approach) using the PK functions plug-in for Microsoft Excel and will be validated in a statistical software such as R or SAS system. Of note, it is planned to baseline-subtract all further concentrations (hours 2-10), and to also subtract potentially occurring negative values from the AUC.

Baseline concentrations will be included as co-variates into the linear mixed model.

Secondary outcomes:

Triglycerides

Triglycerides will be measured in the plasma in mg/dL at baseline (0h) and 2h, 3h, 4h, 5h, 6h, 8h, 10h after test meal intake. Using non-compartmental analysis, repeated measures over time of triglycerides will be summarised as postprandial AUC (trapezoidal approach) using the PK functions plug-in for Microsoft Excel and will be validated in a statistical software such as R or SAS system.

Minor abundant carotenoids:

Isomers of beta-carotene and lycopene will be treated as the all-trans native form, i.e. all chromatographic peak area will be combined if isomers are identified in the plasma-TRL fraction.

If alpha-carotene or other carotenoids such as lutein and beta-cryptoxanthin can be measured (if chromatographic sensitivity is sufficient), AUC in the TRL fraction will also be determined, as described for beta-carotene and lycopene.

They will be accounted for in the analyses as secondary outcomes with similar analysis methodology

Total carotenoids will be produced by summing up all carotenoids measured and analysed as the primary endpoint

Carotenoids after colonic digestion:

Native carotenoids after colonic digestion, as well as excreted degradation products such as apo-carotenoids will be investigated, as far as the analytical capabilities allow. As no previous data exists in this respect, this part will be of highly explorative character.

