5.2 Analysis methods

The primary endpoint, AUC of either lycopene or beta carotene will be analysed using a linear mixed model using randomization sequence and treatment (test meal) as fixed terms and patient within sequence as a random term taking into account the cross-over design as described in chapter 5 of "Cross-Over Trials", Senn (2002). Baseline will be included as a co-variate.

Assumptions of normality and equality of variance will be verified by normality plots and boxplots, respectively. If data is non- normally distributed, log transformation will be attempted.

Non-parametrical analysis (Friedman tests followed by Wilcoxon- Mann- Whitney test) may be chosen in case data is not normally distributed, if log-transformation is not successful, though based on earlier studies data normally follows normal distribution.

The secondary endpoints - triglycerides, and if feasible additional carotenoids (see 5.1 above) will be analysed by the same methodology.

A linear mixed model will be first performed for each main outcome, with either baseline corrected AUC of lycopene or beta-carotene as the observed, dependent variable, and randomization sequence, test-meal as the independent variable (fixed factor) and patient within sequence as random factor. Pairwise comparisons of the intervention will be performed by means of Tukey's post-hoc test. Additionally, sensitivity analysis with the original outcomes (lycopene or beta-carotene) as dependent, randomization sequence, test meal and baseline concentration of the outcome as fixed factors and patient within sequence as random factor. 95% confidence intervals will be reported for the main outcomes.

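### If normality fails, the SAP attempts a log of a primary AUC that may be negative, gives no rule for values at or below zero, and contradicts Protocol 11

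*SAP*

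**What the plan says.** **Endpoint.** SAP 2.2(c): "Data will be baseline subtracted – conc. at time 0 will be subtracted from all later values". Under 2.2(d), where the curve falls below baseline, "this area will be subtracted from the positive area". SAP 5.1 plans "to also subtract potentially occurring negative values from the AUC". Protocol 11 agrees: "Negative values, if occurring, will be included as such". SAP 5.2 runs the mixed model "with either baseline corrected AUC of lycopene or beta-carotene as the observed, dependent variable".

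**Response to non-normality in the SAP.** SAP 2.2(b): "Verifying whether data is normally distributed. If not, log-transformation will be attempted". SAP 5.2: "If data is non- normally distributed, log transformation will be attempted". If the log does not succeed, SAP 5.2 permits, without requiring, a Friedman test with Wilcoxon-Mann-Whitney follow-up. The check itself is by normality plots and boxplots, with no numerical criterion.

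**Response to non-normality in the Protocol.** Section 11 excludes the log twice, once in the words "Log-transformation will not be carried out". It goes straight to an optional Friedman test followed by t-tests. Section 6 is milder and says only that transformation is not needed.

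**Sensitivity analysis.** SAP 2.2(c) and 5.2 already plan an analysis of the unsubtracted outcome with the baseline concentration as covariate.

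**The concern.** The plan provides for negative values of the endpoint and also names a transformation that cannot accept them. It gives no offset, no exclusion rule and no definition of an unsuccessful log. The order of the SAP 2.2 list (log at (b), baseline subtraction at (c)) leaves unclear which AUC would be logged. The Protocol excludes the step altogether. SAP 2.1 refers only matters it does not itself cover back to the Protocol, so it does not settle the conflict.

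At stake is the form of the primary result. If the log cannot be computed, the analyst chooses with the data in hand between the untransformed model and a rank analysis. The rank route has no sequence term, baseline covariate or Tukey comparisons, and none of the model-based intervals behind the 95% confidence intervals promised in SAP 5.2. If the Wilcoxon-Mann-Whitney test is meant as the unpaired rank-sum test, it also discards the within-man pairing that the crossover was designed to use.

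**Working it through.** **1. Range of the endpoint.** Sampling runs from 0 to 10 h. Subtracting C(0) from every later value gives, by the trapezoidal rule,

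baseline-corrected AUC = raw AUC(0–10 h) − 10 × C(0).

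This is at or below zero whenever the time-averaged concentration over 10 h does not exceed the 0 h value. For illustration, ln(1.2) = 0.18, ln(0.8) = −0.22, and ln(−0.05) is undefined. One non-positive AUC among the 24 × 3 = 72 per carotenoid is therefore enough to defeat a plain log for that record.

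**2. Which AUC is logged?** There are two readings.

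- *The raw AUC is logged, following the order (b) then (c).* It is positive if concentrations are, so no domain problem arises. But SAP 5.2 names the baseline-corrected AUC as the dependent variable, and a subtraction made after the log is no longer on the concentration scale.
- *The baseline-corrected AUC is logged, following SAP 5.2.* The log is undefined for values at or below zero.

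The list is not strictly chronological, since (a) computes the AUC before (c) subtracts concentrations. The order alone does not decide between the readings.

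**3. The plan's own figure.** SAP 2.6 states 96% power at n = 24 and 83% at n = 18, for a difference of 4, SD of paired differences 4 and two-sided alpha 0.05/6 = 0.00833. A noncentral t calculation with ncp = (4/4)√n (4.90 and 4.24) and df = n − 6 gives 96.2% and 83.5%. The figures reproduce. They presume a paired analysis on the untransformed scale.

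**4. How often would the gap matter?** The documents give the SD of paired differences, which implies a within-subject SD of 4/√2 = 2.83 if errors are equal and independent. They give no between-subject SD, so the rest is assumption.

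First, any non-positive value. If each AUC has probability p of being non-positive, independently, P(at least one of 72) = 1 − (1 − p)^72. For p = 0.1%, 1% and 5% this is 7%, 52% and 98%.

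Second, the joint event, from 4,000 simulated trials per row with meal means 20, 24 and 24. A Shapiro-Wilk test at 0.05 on meal-centred values stands in for the SAP's plots.

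| Subject distribution | Spread | Within SD | Any AUC ≤ 0 | Normality rejected | Both |
|---|---|---|---|---|---|
| Normal | SD 4 | 2.83 | 0.1% | 10% | 0.1% |
| Normal | SD 8 | 2.83 | 22% | 28% | 8% |
| Normal | SD 12 | 2.83 | 75% | 40% | 28% |
| Normal | SD 16 | 2.83 | 95% | 49% | 45% |
| Log-normal | log-SD 0.4 | 2.83 | 0.6% | 73% | 0.4% |
| Log-normal | log-SD 0.6 | 2.83 | 6% | 93% | 5% |
| Log-normal | log-SD 0.8 | 2.83 | 24% | 99% | 23% |
| Log-normal | log-SD 1.0 | 2.83 | 46% | 99.7% | 45% |
| Log-normal | log-SD 0.8 | 6 | 80% | 96% | 76% |
| Log-normal | log-SD 1.0 | 6 | 90% | 99% | 89% |

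Two cautions apply. In the normal rows the rejection rate exceeds 5% because the test pools three correlated values per man, so those joint figures depend on how normality is checked. In the last two rows, a within-subject SD of 6 alone implies an SD of paired differences of 6 × √2 = 8.5, well above the SAP's 4.

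**5. Cost of the fallback.** This uses 3,000 simulations at difference 4, SD of differences 4, alpha 0.00833 and n = 24, with normal data.

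| Between-subject SD | Paired t | Wilcoxon signed-rank | Unpaired Mann-Whitney |
|---|---|---|---|
| 2 | 97% | 96% | 89% |
| 4 | 97% | 96% | 50% |
| 8 | 97% | 96% | 1% |

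A paired rank test costs about one point of power. The unpaired test can lose nearly all of it.

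**The case against.** The strongest defence is that SAP 5.2 already sets out a path: fit the model, try a log if the data are non-normal, and consider rank tests if the log does not succeed. An undefined log is naturally an unsuccessful one, so the plan is not silent. That is a fair reading, but it does not cure the problem. The analysis would leave the model because of a sign, not because of how well the model fits, and the permissive wording still leaves the choice open.

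The two technical complaints are also alternatives. If the raw AUC is logged there is no domain problem; if the corrected AUC is logged the order is irrelevant. This stands, and it supports asking for one stated rule.

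A reader might infer that a single man with a net fall is enough to push the primary analysis off its model. The documents do not support that. The mixed model takes negative AUCs as they are, the log is tried only under non-normality, and the fallback is optional. For the same reason the chance of any negative value is not the chance of the problem: in the normal SD 12 scenario these are 75% and 28%.

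A reader might also expect low absorbers to be dropped or an arbitrary constant added. Neither document proposes either, and a net-negative visit can occur on any meal, including control.

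Finally, Protocol 11 opens the Friedman route on non-normality alone. Deleting the log would therefore not by itself protect the primary model. This stands, and the fix has to cover it.

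**Conclusion.** The point holds in conditional form. On the text alone, without any assumed number, the SAP prescribes an undefined operation for part of the endpoint's permitted range, gives no rule for it, leaves unclear which AUC is meant, and conflicts with Protocol 11. Protocol 6 is not a second prohibition, since it states only that transformation is not needed.

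The practical size is uncertain. The trigger is non-normality together with at least one AUC at or below zero. Its probability depends on a between-subject SD that the documents do not give and on how normality is judged. With the within-subject SD implied by SAP 2.6 it runs from 0.1% to about 45% in the scenarios tried, and it is higher with noisier data. If the trigger occurs and the rank route is taken, the estimates and intervals from the planned model are lost. The power loss is small for a paired rank test and potentially near total for an unpaired one. This should be corrected in the SAP; it is not a fault in the trial's design.

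**What to change.** - Delete the log step for the baseline-subtracted AUC in SAP 2.2(b) and 5.2, to match Protocol 11.
- State that the untransformed baseline-corrected AUC, negative values included, analysed in the linear mixed model, is the primary analysis whatever the normality check shows.
- Label as sensitivity analyses only: the already planned unsubtracted-AUC model with baseline as covariate, and a paired rank analysis (Friedman, then Wilcoxon signed-rank in place of Wilcoxon-Mann-Whitney).
- Amend the non-parametric fallback in Protocol 11 to the same status, so that both documents give one answer.

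A log of the unsubtracted AUC is not a good substitute. Protocol 11 excludes that log too, and a logged 0 h covariate could itself be undefined if the washout brings a baseline value to zero.

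The cost is a few lines of wording and no new data. The downside is that under marked skewness the primary result rests on the robustness of the untransformed model, which the sensitivity analyses would help a reader judge.

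### The normality triggers are worded on the data rather than on model residuals, so skewed AUC levels between men could needlessly move a sound paired analysis to a ratio scale or an unpaired rank test

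*SAP*

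**What the plan says.** SAP 2.2 lists steps in order. The AUC is computed in (a). Step (b) is "Verifying whether data is normally distributed. If not, log-transformation will be attempted". Baseline subtraction follows in (c), the handling of negative area in (d) and the baseline covariate in (e).

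SAP 5.2 describes a linear mixed model with "patient within sequence as a random term taking into account the cross-over design". It then says "Assumptions of normality and equality of variance will be verified by normality plots and boxplots, respectively", without naming what is plotted. The next sentence sets the action: "If data is non- normally distributed, log transformation will be attempted". If the log does not succeed, "Non-parametrical analysis (Friedman tests followed by Wilcoxon- Mann- Whitney test) may be chosen in case data is not normally distributed".

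Protocol section 11 says "Normal distribution will be verified by Q-Q-plots and Kolmogorov-Smirnoff tests", again without naming the object. Its rank fallback (Friedman, then individual t-tests) also depends on the data not being normal. On the log it says the opposite of the SAP: "Log-transformation will not be carried out".

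Both documents add that, from earlier studies, such data usually are normal. Neither uses the word residuals.

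**The concern.** Each man eats all three meals, so his own absorption level drops out of every meal contrast when his data are complete. How that level is distributed between men, skewed or not, does not affect the validity of the contrast. The distribution of the pooled AUCs, however, is largely the distribution of those levels. A check made on the AUCs can therefore fail when the model is sound. The 72 pooled values (24 men x 3 meals) are also not independent, as a Kolmogorov-Smirnov test assumes.

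What is at stake is the form of the primary result. A log analysis reports a ratio, whereas the trial was sized on a difference. The log also does not exist if the net AUC is zero or negative, which SAP 2.2(d) makes possible by subtracting negative area. The rank route ends in a test for two independent samples, which discards the pairing. Two analysts reading the same text could check different quantities and report different primary analyses.

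**Working it through.** **1. The plan's own power (SAP 2.6).** Inputs: difference 4 (20 vs 24), SD of paired differences 4, N = 24, two-sided alpha 0.05/6 = 0.00833.
- N = 24: noncentrality 4/(4/√24) = 4.90; with df = 24 − 6 = 18, power is 96.2% (stated 96%).
- N = 18: noncentrality 4/(4/√18) = 4.24; with df = 18 − 6 = 12, power is 83.5% (stated 83%).

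Both figures reproduce. Neither uses a between-man SD, because the sizing is on paired differences.

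**2. What a check on AUCs looks at.** Write AUC = mean + man effect + meal effect + error. The difference between two meals in one man contains only the meal effects and two errors. The within-man SD is 4/√2 = 2.83, a variance of 8. The documents give no between-man SD, so a CV of 30, 50 or 70% around the control level of 20 is assumed, that is, an SD of 6, 10 or 14. Leaving meal effects aside, the between-man share of the AUC variance is:
- CV 30%: 36/(36 + 8) = 82%
- CV 50%: 100/(100 + 8) = 93%
- CV 70%: 196/(196 + 8) = 96%

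A normality check on AUCs is thus mostly a check on how men differ.

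**3. How often it would fire, and the cost.** Simulated trials had 24 men x 3 meals, log-normal man levels, normal additive within-man error and a true difference of 20%, tested at 0.00833. The within-man model is valid by construction. A numeric 5% test stands in for the SAP's plots. A flagged trial goes to the log scale, or to the unpaired rank test if any AUC is zero or negative.

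| Between-man CV | 30% | 50% | 70% |
|---|---|---|---|
| AUCs flagged, plain Kolmogorov-Smirnov | 2% | 16% | 37% |
| AUCs flagged, Shapiro-Wilk | 35% | 74% | 91% |
| Within-man residuals flagged | 3-4% | 3-4% | 3-4% |
| Power, untransformed throughout | about 97% | about 97% | about 97% |
| Overall power, plain Kolmogorov-Smirnov trigger | 97% | 95% | 90% |
| Overall power, Shapiro-Wilk trigger | 96% | 91% | 78% |

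**4. The rank follow-up.** Take normal between-man spread with SD 5.66 as an example.
- Paired standard error: 4/√24 = 0.82, so the expected statistic is 4/0.82 = 4.9.
- Unpaired SD: √(5.66² + 8) = 6.33. Standard error: 6.33 x √(2/24) = 1.83. Expected statistic: 4/1.83 = 2.2, below the two-sided normal critical value of 2.64.

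In simulation the power was 98% for the paired mixed model, 96% for a paired signed-rank test and 16% for Wilcoxon-Mann-Whitney. The loss comes from dropping the pairing, not from using ranks.

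**5. The opposite error structure.** If error and meal effect scale with a man's level, untransformed power is 91/83/74% at CV 30/50/70%, against 93-94% on the log scale. A trigger based on residuals keeps 90-97% under both structures.

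**The case against.** The strongest reply is that SAP 5.2 places its sentence on assumptions of normality directly after the mixed model, where it reads naturally as the assumptions of that model. This stands in part. A reader might infer that the SAP deliberately tests raw AUCs instead of residuals, but the text does not say so. It is ambiguous in 5.2, silent in the protocol, and points to the data only through the order of steps in 2.2(b) and the wording of the triggers.

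The size is also open to challenge, and rightly. The SAP check is graphical and has no 5% threshold. Kolmogorov-Smirnov appears only in the protocol, which rules out the log; Shapiro-Wilk appears in neither document. The rank route is discretionary and comes only after the log has failed. Both documents expect normal data. The flag rates are therefore a proxy, and the range between the two tests is wide.

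A reader might also infer that the log route is always the weaker one, or that the untransformed model should stay primary whatever happens. Neither is supported. The log analysis stays paired and loses little when spread is modest, and step 5 shows that it is the better scale under proportional error. The documents do not say which error structure holds.

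What remains is that the action is tied to the wrong quantity in the wording, and that the last fallback discards the pairing.

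**Conclusion.** The concern holds as a defect of wording with a possible, not certain, effect on the primary analysis. Nothing in the documents shows that the planned mixed model is invalid or that the trial is underpowered.

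The size rests on an assumed between-man CV and shape, on normal additive within-man error, and on a numeric test in place of plots. On those terms the loss is negligible at CV 30% (97-96% against about 97%), small to moderate at 50% (95-91%) and up to about 19 points at 70% (90-78%). The low end includes the unpaired rank test where the log is undefined. Under proportional error the move to the log is a gain. The change from a difference to a ratio occurs whenever the log route is taken, whatever the power. Severity: minor to moderate.

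**What to change.** - In SAP 2.2(b), SAP 5.2 and Protocol section 11, state that normality and equal variance are judged on the conditional (within-man) residuals of the fitted mixed model, by Q-Q and residual plots. Place this after model fitting, on the baseline-corrected AUC.
- State that only failure of that check triggers the alternative, and set out the alternative in advance, including what is done when a net AUC is zero or negative.
- Reconcile the SAP, which attempts a log transformation, with the protocol, which excludes it.
- For any rank fallback, replace the Wilcoxon-Mann-Whitney follow-up with a paired rank test, such as Wilcoxon signed-rank, and align the protocol's follow-up tests with it.
- Do not require the untransformed model to stay primary whatever the residuals show.

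The cost is wording in two documents, ideally settled before outcome data are seen. No extra participants, visits or samples are needed.
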